PML Progressive Multifocal Leukoencephalopathy

PRO Patient Reported Outcomes

PY Patient Years

QoL Quality of Life

RCT Randomized Control Trial

RMS Relapsing Multiple Sclerosis

SAE Serious Adverse Event

SC Steering Committee

SDMT Symbol Digit Modalities Test

SF-36 36-Item Short Form Health Survey

SmPC Summary of Product Characteristics

CCI

TEAE Treatment-Emergent Adverse Event

TB Tuberculosis

TSQM v1.4 Treatment Satisfaction Questionnaire Medication version 1.4

VZV Varicella Zoster Virus

WOCBP Women of Child Bearing Potential

1 Synopsis

Clinical Trial Protocol Number	MS700568 0021
Title	A 2-year prospective study to assess health-related quality of life in subjects with highly-active relapsing multiple sclerosis treated with Mavenclad®
Trial Phase	IV
IND Number	Not applicable
FDA covered trial	Not applicable
EudraCT Number	2017-002632-17
Coordinating Investigator	PPD
Sponsor	Merck KGaA, [name]
Sponsor Legal Representative in the European Union	Merck KGaA, [name]
Trial centres/countries	Europe (including, but not limited to): Austria, Belgium, Czech Republic, Denmark, Finland, France, Greece, Hungary, Italy, Lithuania, Netherlands, Norway, Poland, Portugal, Spain, Slovakia, Sweden, UK, Australia
Planned trial period (first subject in-last subject out)	First Subject First Visit: Q2/2018 Last Subject Last Visit: Q4/2021
Trial Registry	EU Clinical Trials Register ClinicalTrials.gov

Objectives:
 
Primary:
 
 To assess the health-related quality of life (HRQoL) through the MSQoL-54 scale in highly-active relapsing multiple sclerosis (RMS) subjects treated with Mavenclad® for 2 years (24 months) 
Secondary:
 
 To assess treatment satisfaction through the TSQM v1.4 questionnaire in highly active RMS subjects at 6 months of treatment with Mavenclad® 	

CCI

Methodology: This will be an open label, single arm, exploratory, multicentre, 2-year Phase IV study.

Subjects will attend visits for assessments at Baseline and at Months 6, 12, 18, and 24.

Subjects will attend visits for lymphocyte count as per mandatory monitoring at Screening, Baseline and at Months 2, 6, 12, 14, 18 and 24.

Planned number of subjects: 445

Primary endpoint:

- Changes in MSQoL-54 at 24 months compared to Baseline, i.e., the changes in the physical and mental health composite scores

Secondary endpoints:

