Differences in MSQoL-54 physical health and mental health composite scores between the Baseline assessment and the 24-month assessment will be evaluated with mixed-effects linear regression, accounting for within-subject correlation and within-centre/region correlation through a hierarchical model. The model will include all available assessment data up to and including the 24-month assessment and consider time as a categorical covariate. The Full Analysis Set (FAS) will be the primary population. Secondary and tertiary endpoints will be assessed using similar methods. Treatment satisfaction assessed by TSQM v1.4 at 6 months will be evaluated during an interim analysis that will be performed as soon as all enrolled subjects reach 6 months after treatment initiation. The analysis at 6 months will be considered as supportive of the 24 months analysis (main analysis).

Safety analysis:

All safety assessments will be descriptively summarized.

2 Sponsor, Investigators and Trial Administrative Structure

The Sponsor of this clinical trial with Mavenclad® is Merck KGaA, [name].

The trial will be conducted at approximately 120 sites across Europe including Austria, Belgium, Czech Republic, Denmark, Finland France, Greece, Hungary, Italy, Lithuania, Netherlands, Norway, Poland, Portugal, Spain, Slovakia, Sweden, UK, as well as in Australia. The study is open to other countries if there appears a need to increase the recruitment.

The Coordinating Investigator, PPD [REDACTED] represents all Investigators for decisions and discussions regarding this trial, consistent with the International Council for Harmonisation (ICH) Topic E6 Good Clinical Practice (ICH GCP). The Coordinating Investigator will provide expert medical input and advice relating to trial design and execution and is responsible for the review and signoff of the clinical trial report.

Signature pages for the Protocol Lead and the Coordinating Investigator as well as a list of Sponsor responsible persons are in [Section 12.14](#).

The trial will appear in the following clinical trial registries: ClinicalTrials.gov, EU Clinical Trials Register and national registries as per local regulations.

A contract research organization (CRO), PPD [REDACTED] will undertake the operational aspects of this trial with oversight by the Sponsor. Details of such structures and associated procedures will be defined in a separate Integrated Project Management Plan (IPMP).

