The start of COVID-19 pandemic will be defined by country as the earliest date of either the date of the first death from COVID-19 occurred in each country according to the published data by European Centre for Disease Prevention and Control on 26th June 2020 (<https://www.ecdc.europa.eu/en/publications-data/download-todays-data-geographic-distribution-covid-19-cases-worldwide>) or 11th March 2020 (when the WHO declared COVID-19 pandemic).

Visit timing with respect to COVID-19 pandemic

A visit is defined to be performed after the start of COVID-19 pandemic if the visit end date is greater than the start of COVID-19 pandemic date.

Conversion factors

The following conversion factors will be used to convert days into months or years for all observations except Visit related dates:

- 1 month = 30.4375 days,
- 1 year = 365.25 days.

Time window

- Day 1 is the day of start of study medication, the day before is Day -1 (no Day 0 is defined).
- Study day / Treatment day is defined relative to Day 1.

The visit schedule is defined as follows:

- 1 month = 30 days,
- 1 year = 360 days,

relative to the start date of the Baseline Visit for Treatment Course 1 and relative to the start date of the Month 12b Visit as defined in the eCRF (see also Section 15.3) for Treatment Course 2.

In each analysis, should assessment be delayed, subjects' assessment data will be treated as though it occurred at the time point specified (i.e. out of visit windows will be not excluded or adjusted for any analyses) and inferences will be conducted accordingly. Thus, further time windows will not be specified.

All observations from unscheduled Visits will be included only in the analyses of Visit independent summaries (e.g. counts of events, progressions or worst value during Treatment Period) unless for the last assessment available. In this case the missing ET visit will be imputed by the unscheduled visit.

If not specified otherwise, the assessments of the ET visit will be mapped to the nearest next planned post-baseline visit with a missing assessment before or after the ET visit of the individual assessment for all statistical analyses and descriptive summaries. As not all assessments of the ET

are performed at each visit, the different assessments of the ET can be assigned to different visits. If the duration (in days) between the ET visits and two missing planned visits are equal, then the assessment will be assigned to the later visit.

Handling of missing data

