15.3 Clinical Laboratory Evaluation

Lymphocyte counts from local laboratory will be used for summary statistics and shift tables. They will be classified according to the NCI-CTCAE (latest version available). The classification will be derived only from the laboratory results at a given assessment, thus ignoring the underlying syndrome.

The Treatment Course 2 can be delayed because of Lymphocyte count below 800 cells/mm³ at the Month 12 Visit. In this case, the Lymphocyte count can be measured several times between the Month 12 Visit and the start of Treatment Course 2. Lymphocyte counts at or after the visit start date of the Month 12 Visit and before or at the start date of the Treatment Course 2 will be displayed as follows:

- The earliest Lymphocyte count will be assigned to the Month 12 Visit,
- The latest Lymphocyte will be assigned to the Month 12b Visit,
- All other Lymphocyte count will be assigned to unscheduled visits.

A Lymphocyte count can be assigned to the Month 12 Visit and Month 12b Visit, if just one count is available. If the Treatment Course 2 wasn't started, only the earliest Lymphocyte count will be assigned to the Month 12 Visit.

The worst on-study grade (i.e. on or after first study treatment administration) will be summarized considering only subjects with post Baseline laboratory samples: Laboratory tests by NCI-CTCAE grade (0, 1, 2, 3, 4, any).

Lymphocyte counts will be examined for trends using descriptive statistics (mean, SD, median, Q1, Q3, minimum, and maximum) of actual values and changes from Baseline to each scheduled Visit including Month 12b Visit over time. If for a particular visit a different local laboratory than normal laboratory was used (due to COVID-19 pandemic), values collected during that visit will not be included in the descriptive statistics.

Shift tables of Baseline versus endpoint (as well as the worst value at any post-Baseline Visit) will be presented. Abnormalities classified according to NCI-CTCAE toxicity grading (latest version available) will be described using the worst grade.

All Lymphocyte counts will be listed by subject for the SAF.

Positive results of the tuberculosis and serology tests that do not comply with the protocol will be listed.

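### By-visit lymphocyte statistics drop substitute-laboratory counts taken because of COVID-19, with no reason that fits the actual values; all counts should stay in, with a sensitivity table for change from Baseline (minor)

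*SAP*

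**What the plan says.** SAP 15.3 names its source and outputs at the start: "Lymphocyte counts from local laboratory will be used for summary statistics and shift tables". It plans descriptive statistics (mean, SD, median, quartiles, minimum, maximum) "of actual values and changes from Baseline to each scheduled Visit including Month 12b Visit over time". The exclusion follows at once. Its trigger is a visit at which COVID-19 led a subject away from the usual local laboratory to another one. For such a visit, the SAP says, "values collected during that visit will not be included in the descriptive statistics".

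The section gives no reason for the rule. It plans no count of excluded values and no table with them restored. It states no such exclusion for the worst on-study NCI-CTCAE grade or for the shift tables, and it lists all counts by subject. SAP Section 13 groups subjects by a count below 800 cells/mm³ around the start of Course 2, also without a laboratory restriction. SAP Section 7 describes the COVID-19 change to the planned analyses only as added analyses and does not mention this removal.

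On the setting, Protocol Section 2 says: "The trial will be conducted at approximately 120 sites across Europe" and in Australia. Protocol Section 7.1 has the lymphocyte counts done at local laboratory facilities. Neither document gives a number of laboratories or of visits at a substitute laboratory.

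**The concern.** The rule removes observed safety data because of where the sample was read. The same section accepts counts from many local laboratories side by side with no adjustment, and a substitute local laboratory is one more of the same kind. The trigger is also narrow: as written, a change of laboratory for any reason other than COVID-19 leaves the count in. It therefore does not work as a general comparability rule.

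Two things are at stake. Protocol Section 3.3 names severe lymphopenia as an important identified risk, and the affected table is the one planned to show trends in the count over time. If the excluded counts cluster at late visits, the trend after Course 2 rests on fewer subjects than the trend after Course 1. The tables may also fail to agree. A low count from a substitute laboratory could supply a subject's worst grade, yet be missing from the minimum for the visit at which it was taken.

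**Working it through.** The plan states no figure to reproduce. The check has two parts: the logic of the rule, and where on the calendar it can act.

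**Logic, by type of summary**

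- *Actual values.* The by-visit mean, SD, median and minimum combine counts across subjects and laboratories. A subject's count from a substitute laboratory enters in the same way as another subject's count from that laboratory. Nothing in 15.3 separates the two.
- *Changes from Baseline.* A constant laboratory offset cancels within a subject if Baseline and visit come from the same laboratory. It does not cancel after a switch. There is a reason for caution here, which a with-and-without display addresses.

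**Calendar: inputs**

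- Planned N: "Planned number of subjects: 445" (Protocol synopsis).
- Trial period: "First Subject First Visit: Q2/2018 Last Subject Last Visit: Q4/2021" (Protocol synopsis).
- Latest possible pandemic start: "11th March 2020 (when the WHO declared COVID-19 pandemic"), or an earlier date where a country's first COVID-19 death came first (SAP Section 9).
- Post-treatment counts: Months 2, 6 and 12 before Course 2; Months 14, 18 and 24 after it (Protocol Table 3).
- Visit-schedule month: 30 days (SAP Section 9).

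**Assumptions (not in the documents).** Accrual is uniform and there is no dropout. First baseline falls on 1 April or 30 June 2018. Last baseline is the last visit (1 October or 31 December 2021) minus 720 days, minus a further 0, 90 or 180 days for slack or delay. That gives 2 × 2 × 3 = 12 scenarios.

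**Month 24.** The earliest scheduled Month 24 is 1 April 2018 + 720 days = 21 March 2020, or 14 March 2020 at the early edge of the ±7-day window. Both dates follow 11 March 2020, so every scheduled Month 24 visit is exposed.

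**Share of scheduled counts dated after 11 March 2020, range over the 12 scenarios**

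| Visit | Share exposed |
|---|---|
| Month 2 | 0% |
| Month 6 | 0–21% |
| Month 12 | 8–53% |
| Month 14 | 23–64% |
| Month 18 | 55–86% |
| Month 24 | 100% |

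Months 14, 18 and 24 together hold 77% to 96% of all exposed post-baseline counts.

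**Central scenario.** Baselines run from 15 May 2018 to 28 August 2019, which is 471 days. The exposed share v is 164/471 = 35% at Month 12, 224/471 = 48% at Month 14, 344/471 = 73% at Month 18, and 100% at Month 24. Months 2 and 6 are not exposed. The share of exposed counts after Course 2 is (224 + 344 + 471)/(164 + 224 + 344 + 471) = 1039/1203 = 86%.

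Let q be the share of pandemic-era visits done at a substitute laboratory. The documents do not give q, so the values below are assumptions. Retained n = 445 × (1 − q·v).

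| q | Month 12 | Month 14 | Month 18 | Month 24 |
|---|---|---|---|---|
| 5% | 437 | 434 | 429 | 423 |
| 10% | 430 | 424 | 412 | 400 |
| 20% | 414 | 403 | 380 | 356 |
| 30% | 399 | 382 | 347 | 312 |

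In terms of precision, the standard error of a visit mean would rise by 1/√(1 − q·v) − 1. At Month 24 (v = 1) this is 5.4%, 11.8% and 19.5% for q = 10%, 20% and 30%. At Month 12 the same q give only 1.8%, 3.7% and 5.7%. The SAP plans no standard error for these counts, so the retained n is the more relevant measure.

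**The case against.** The strongest reply is that pooling laboratories across subjects differs from changing laboratory within a subject, and that like-for-like laboratories are a defensible choice for change from Baseline. That stands for the changes. It does not reach the actual values, which the rule drops as well.

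A second reply is that the severe-lymphopenia signal is covered elsewhere. The worst-grade summary, the shift tables and the grouping in SAP Section 13 carry no stated exclusion, and all counts are listed. The opening sentence of 15.3 names summary statistics and shift tables separately, so the natural reading is that shift tables keep every count. This largely stands and is the main reason why the point is minor. The SAP does not say so explicitly, however, and the possible mismatch with the visit minima remains.

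A third reply is that the study is exploratory and single-arm, and that the affected output is one descriptive table with no test, interval or decision rule. That also stands and limits the severity.

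A reader might go further than the documents allow in three ways:

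- *That about 120 laboratories are pooled.* The documents give approximately 120 sites; one laboratory per site would be an assumption.
- *That precision falls by 5% to 20% at the late visits generally.* Those figures apply to Month 24 only, for assumed values of q.
- *That the trend is biased.* Nothing in the documents links the change of laboratory to the count. Bias arises only if the two are related, and neither its direction nor its size can be stated.

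**Conclusion.** The point holds as a minor one. For actual values the exclusion has no stated rationale, and it sits badly with the unadjusted pooling in the same section. For changes from Baseline the within-subject switch is a fair reason for a sensitivity check, but not for deletion.

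That all scheduled Month 24 counts are exposed follows from the planned start date, the 30-day month and the pandemic start date. That the exposure falls mainly after Course 2 also needs the accrual assumption, and part of it falls at Month 12, before Course 2. The loss itself depends on the unreported number of substitute-laboratory visits and could be close to nil.

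**What to change.** Reword SAP 15.3 as follows:

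1. Include all lymphocyte counts in the by-visit statistics for actual values.
2. Present changes from Baseline with all counts, and repeat that table without substitute-laboratory values as a sensitivity check.
3. Flag substitute-laboratory values in the subject listing and report their number per visit.
4. State that the worst-grade and shift tables use all counts.

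The cost is a wording change, one extra table and slightly more between-laboratory noise in the within-subject changes. No new data are needed.

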15.4 Vital Signs

The maximum changes of vital sign measurements from Baseline to maximum change after start of 1st treatment will be grouped as follows:

Heart rate increase from Baseline <100 bpm ; ≥ 100 bpm	≤20 bpm, >20 – 40 bpm, >40 bpm
Heart rate decrease from Baseline <100 bpm ; ≥ 100 bpm	≤20 bpm, >20 – 40 bpm, >40 bpm
SBP increase from Baseline <140 mmHg; ≥ 140 mmHg	≤20 mmHg, >20 – 40 mmHg, >40 mmHg
SBP decrease from Baseline <140 mmHg; ≥ 140 mmHg,	≤20 mmHg, >20 – 40 mmHg, >40 mmHg
DBP increase from Baseline <90 mmHg; ≥ 90 mmHg	≤20 mmHg, >20 – 40 mmHg, >40 mmHg
DBP decrease from Baseline <90 mmHg; ≥ 90 mmHg,	≤20 mmHg, >20 – 40 mmHg, >40 mmHg

For each subject the worst change during the treatment period will be considered. Missing values will be presented as a separate category.

The following summaries will be prepared for vital sign parameters as grouped above considering only subjects with post Baseline values:

- Maximal Shifts (changes in categories),
- Listing of highest change per subject.

15.5 Other Safety or Tolerability Evaluations

The results of the physical examination will not be presented in any statistical analysis or listing. Abnormalities occurring or worsening during the study will be reported as AE.

Safety Findings during Central Review are reported back to the sites for further clinical assessment and reporting as AE, as outlined in the Review Charter. Thus, no separate statistical reporting of the Safety MRI central review data will be done.

Positive pregnancy tests or pregnancy tests not done without a reason will be listed for the SAF.

16 Analyses of Other Endpoints

Not applicable.

17

References

Ulm K. A simple method to calculate the confidence interval of a standardized mortality ratio. American Journal of Epidemiology 1990;131(2):373-375.

VERMERSCH, P. et al. Teriflunomide versus subcutaneous interferon beta-1a in patients with relapsing multiple sclerosis: a randomised, controlled phase 3 trial. Mult Scler, v. 20, n. 6, p. 705-16, May 2014. ISSN 1477-0970. Disponível em: <<https://www.ncbi.nlm.nih.gov/pubmed/24126064>>.

VICKREY, B. G. et al. Comparison of a generic to disease-targeted health-related quality-of-life measures for multiple sclerosis. J Clin Epidemiol, v. 50, n. 5, p. 557-69, May 1997. ISSN 0895-4356. Disponível em: <<https://www.ncbi.nlm.nih.gov/pubmed/9180648>>.

VICKREY, Barbara G. Multiple sclerosis quality of life (MSQOL)-54 instrument. *Los Angeles: University of California, Los Angeles*, 1995.

QuintilesIMS, User Manual for the Treatment Satisfaction Questionnaire for Medication (TSQM), Version 1.0, July 2017.

Parmenter, B. A., et al. The utility of regression-based norms in interpreting the minimal assessment of cognitive function in multiple sclerosis (MACFIMS). J. Int. Neuropsychol. Soc. 16, 6-16 (2010).

18

Appendices

CCI

Subjects who have taking any of the listed DMDs according to the “Relevant Previous Medication” eCRF page will be categorized as DMD pre-treated. All other subjects will be considered as pre-treatment naïve. The list may be extended during medical review in case that new or other DMDs will be applied during the study.

Signature Page for VV-CLIN-279857 v6.0

Approval

PPD

21-Sep-2021 15:07:53 GMT+0000

Signature Page for VV-CLIN-279857 v6.0
